## 6.2 Primary and Secondary Endpoints/Outcome Measures

#### 6.2.1 Primary Endpoints/Outcome Measures

The primary endpoint of the study is the proportion of movements, as identified by the scan operator, that are successfully detected by the wearable device and the pregnant women, at weeks 32, 34, 36, and 38 of pregnancy. These are the sensitivity rates of the device and pregnant women in detecting foetal movements, treating the scan operator detected movements as the "true" movements.

Fetal movement information noted on the scan would be collected by the operator pressing a foot pedal each time a movement is noted. If the movement persists, another event would be recorded. Fetal movements will be defined as any movement noted by the scan operator. Therefore, a combination of both trunk movements and limb movements will be recorded by the scan operator.

Maternal fetal movements noted would be collected by the mum pressing a button when she felt the movement.

The device will collect movements when the piezoelectric fabric is distorted by fetal movements. Maternal movements such as breathing and vessel pulsation will be filtrated out by software.

All three movements, device, maternally perceived and scan operator recorded will be recorded over 20 mins. The data will be time-stamped to allow matching of the movements, allowing for a degree of error (±500ms) to account for the reaction time of the mother and sonographer.

Raw voltage data collected by the device will be processed and converted to binary movements using an independent "training" subset of the data.

CONFIDENTIAL

Page 9 of 29

Version 2 April 12th 2021

Four separate scans will be undertaken 2 weeks apart. We would aim for these to be in 32nd, 34th, 36th, 38th week. With a margin of flexibility of one week.

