#### 9 STATISTICS

#### 9.1 Description of Statistical Methods/ Sample size

#### 9.1.1 Analysis of Primary Endpoint

This is a pilot study to test KYMIRA's device on human subjects for the first time, with the primary outcome of interest being its effectiveness in detecting fetal movements, as identified by the operator scanning, compared with those detected by the pregnant women.

The analysis of the primary endpoint will therefore be a comparison of the proportion of movements, as identified by the scan operator, that are successfully detected by the wearable device compared with the proportion detected by the pregnant women, at each of weeks 32, 34, 36, and 38 of pregnancy separately.

The data to be analysed are the binary (Yes/No) outcomes for the device and the mother indicating whether each of the scan operator movements was successfully identified. There will be an outcome for the device and the mother (Yes/No, i.e., Detected/Not detected) for the same scan operator-identified movement. The data are therefore paired and a McNemar's test of paired proportions will be conducted to detect a difference in the proportions of movements detected by the device compared with the mother, if such a difference exists.

The same analysis will be repeated for the week 32, 34, 36 and 38 visit movements separately. The movements at a particular visit (either week 32, 34, 36 or 38) will be collated across the pregnant women for analysis. The repeated foetal movements for a given pregnant woman during a particular scan will be treated as independent.

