## 9.1.1.1 Sample Size Determination

Previous studies that compared the number of fetal movements observed by ultrasound and those perceived by mothers during the 3rd trimester (Brown R, 2016) (Hertogs K, 1979) found the later to be highly varied; with different studies reporting different average fractions in the range of 0.16 to 0.44 (Hertogs K, 1979). Hence, we calculated the sample size for an

CONFIDENTIAL

Formatted: Not Highlight

Formatted: Superscript, Not Highlight

Formatted: Not Highlight

Page 17 of 29

Version 2 April 12th 2021

assumed sensitivity rate of 44% for the pregnant mothers, corresponding with the most conservative estimate, i.e., to ensure adequate power. Based on the initial simulation tests of our device, we expect it to detect 0.8 to 0.9 fraction of the fetal movements. Allowing for a potentially lower detection rate in clinical practice, we assumed a sensitivity rate of 60% for the wearable device, again corresponding a larger sample size to ensure sufficient power.

For a single visit (week 32, 34, 36 or 38), based on a two-sided McNemar's test with a 5% significance level and 90% power, 395 movements are required (according to Lachenbruch (1992) (Lachenbruch, 1992) and based on the minimum estimate of the phi correlation r). Each pregnant woman is expected to have a minimum of around 10 foetal movements per 20 minute scan, as detected by the sonographer, therefore (rounding up) approximately 40 subjects are required for the study analysis.

In addition, an independent "training" subset of the data are required for calibrating the device. It is estimated that 3 subjects will be required for this purpose (i.e., approximately 30 movements), taking the number of subjects in the study to 43. Allowing for a drop-out rate of approximately 20%, a final sample size of 54 subjects (again rounding up) are estimated to be required for recruitment into the study. As the sample size required is based upon the number of foetal movements, if a different number of movements per mother is observed than assumed, the number of subjects recruited will be amended to ensure an appropriate total number of movements available for analysis.

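### The operator re-logs a persisting movement but the mother is not told to press again, which understates her sensitivity and could tilt the primary comparison towards the device

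*Protocol*

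**What the plan says.** Section 6.2.1 sets three recording rules.

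- **Operator (reference):** a foot-pedal press for each movement seen, and "If the movement persists, another event would be recorded". No re-logging interval is given.
- **Mother:** "Maternal fetal movements noted would be collected by the mum pressing a button when she felt the movement". Nothing is said about pressing again, or holding the button, while a movement continues.
- **Device:** "The device will collect movements when the piezoelectric fabric is distorted by fetal movements". Raw voltage is later converted to binary movements with a training subset. How one persisting movement is divided is not stated.

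The three time-stamped series are then matched, "allowing for a degree of error (±500ms) to account for the reaction time of the mother and sonographer". Operator events are taken as the truth. Section 9.1.1 makes the operator event the unit of the primary analysis: "There will be an outcome for the device and the mother (Yes/No, i.e., Detected/Not detected) for the same scan operator-identified movement". The paired outcomes go into McNemar's test, separately at weeks 32, 34, 36 and 38. Section 9.1.1.1 plans on an "assumed sensitivity rate of 44% for the pregnant mothers" and 60% for the device.

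**The concern.** The reference and one of the two comparators may be counting different things. The operator's rule weights a movement by how long it lasts. The mother's rule, read naturally, counts it once. Each extra operator event is a fresh opportunity for her to be scored as having missed, although she may have felt and reported that movement.

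McNemar's test uses only the discordant pairs. If the device signal continues through a long movement and is credited at each re-log, the repeats fall in the cell where the device detected and the mother did not. Part of the primary result would then reflect the press instructions and not the ability to detect movement. Presses that were never requested cannot be recovered at analysis.

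**Working it through.** **1. The plan's own figure.** Section 9.1.1.1 gives sensitivities of 0.44 and 0.60, two-sided 5% significance, 90% power and minimum phi.

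- Both detect: max(0, 0.44 + 0.60 - 1) = 0.04.
- Discordant cells: 0.60 - 0.04 = 0.56 and 0.44 - 0.04 = 0.40; sum 0.96, difference 0.16.
- n = (1.960 + 1.282)² × 0.96 / 0.16² = 394.03, rounded up to 395.
- 395/10 = 39.5, so 40 women; 40 + 3 = 43; 43/0.8 = 53.75, so 54.

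The stated 395 and 54 reproduce. The sample-size arithmetic is not in question.

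**2. What one press can match.** A tolerance of ±500 ms around a press spans 1 second. One press can match two pedal presses only if they lie within 1 second of each other and many-to-one matching is allowed. Otherwise a movement logged k times and pressed once gives at most one hit and k-1 misses. If her press is more than 500 ms from every pedal press, it gives no hit at all.

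**3. Size, under assumptions.** Let f be the share of movements that persist and k the operator events per persisting movement. The protocol gives neither. Per movement there are (1 - f) + fk operator events and, with one press per felt movement, at most one maternal hit:

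maternal sensitivity per event = sensitivity per movement / [(1 - f) + fk]

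Suppose that mother and device each truly detect 60% of movements, and that the device, when it detects a movement, is credited on every re-logged event. The device then still scores 60%, provided it detects short and persisting movements equally well.

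| f | k | events per movement | mother, true 60% | spurious gap (points) | mother, true 44% |
|---|---|---|---|---|---|
| 0.1 | 2 | 1.1 | 54.5% | 5.5 | 40.0% |
| 0.2 | 2 | 1.2 | 50.0% | 10.0 | 36.7% |
| 0.2 | 3 | 1.4 | 42.9% | 17.1 | 31.4% |
| 0.5 | 2 | 1.5 | 40.0% | 20.0 | 29.3% |

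The design difference is 60 - 44 = 16 points.

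**4. Effect on the test.** With d the difference and s the sum of the discordant proportions, the chance that McNemar's test on 395 events favours the device is about Φ[(√395·d - 1.96√s)/√(s - d²)]. This treats events as independent, as the protocol does. For f = 0.2, k = 2:

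- Independent pairing: discordant cells 0.30 and 0.20, so d = 0.10, s = 0.50, probability 0.81.
- Minimum phi: cells 0.50 and 0.40, so d = 0.10, s = 0.90, probability 0.55.

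The same calculation gives 0.22 to 0.34 for f = 0.1, k = 2, and 0.94 to 1.00 for f = 0.2, k = 3. In all of these cases the two are equally good per movement.

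**5. The other device reading.** If the device also yields one event per movement, both rates are divided by the same factor. Equal detectors stay equal. With true rates of 60% and 44% and f = 0.2, k = 2, they become 50.0% and 36.7%, a gap of 13.3 points where the true gap is 16.

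**The case against.** The strongest reply is that the protocol is silent on repeat presses by the mother and does not forbid them. A woman who feels a movement continue may well press again, and the loss then shrinks. This stands: one press per felt movement is the natural reading, not a stated rule.

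Second, the direction of any bias in the difference is not established. That the device keeps registering through a long movement is an inference, because the conversion of voltage to binary movements is left undefined. This also stands, and step 5 shows its consequence.

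Third, the 20-point gap needs half of all movements to be logged twice, and milder assumptions give gaps below 16 points. It is one scenario in a range.

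Fourth, re-logging intervals, merging gaps and matching rules are commonly left to a statistical analysis plan, and this is a pilot. Their absence is not the point here. The protocol itself fixes unequal capture instructions for the reference and one comparator, and no analysis rule can restore presses that were not asked for.

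**Conclusion.** The point holds in a limited form. Following the written rules in their natural sense understates maternal sensitivity per movement, and nothing elsewhere in the protocol corrects this. The primary comparison could be biased towards the device, on the condition that the device is credited on re-logged events. If it is not, both sensitivities fall together and the difference is much less affected.

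A reader might infer that the protocol limits the mother to one press, that a device advantage is certain, or that the artefact exceeds the planned 16 points. The documents support none of these. Repeat presses are not excluded, the device's event rule is undefined, and f and k are not given. The range of about 5 to 20 points rests on assumed f and k, one press per felt movement and full device credit on repeats.

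Treating repeated movements within a scan as independent is a separate issue and adds nothing to this conclusion.

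**What to change.** Before the first scan, write one press rule in section 6.2.1 for both pedal and button: either one press per movement onset for both, or repeat presses at the same stated interval for as long as the movement continues. State that the device signal is converted to events by that rule.

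As a sensitivity analysis, merge operator events closer than a pre-set gap into one episode scored once, and merge maternal and device events in the same way. This should not be the primary analysis: pedal presses do not record when a movement ends, and a long episode makes chance matches easier.

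The wording change and the added instruction to the mother cost almost nothing. The real cost is in the count. With one press per onset, or with merging, events per scan may fall below the assumed 10. If those 10 are pedal events, and 395 is kept:

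- f = 0.1, k = 2: 10/1.1 = 9.09 per scan; 395/9.09 = 43.5, so 44 women; (44 + 3)/0.8 = 58.75, so 59 recruited.
- f = 0.5, k = 2: 10/1.5 = 6.67 per scan; 395/6.67 = 59.3, so 60 women; (60 + 3)/0.8 = 78.75, so 79 recruited.

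The plan is 54. If the 10 already means distinct movements, nothing changes. Section 9.1.1.1 allows recruitment to be adjusted to the observed count, so it should say which unit the 10 refers to and restate the figure.

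### A single ±500 ms matching tolerance with no lag alignment can lose true device and maternal detections at different rates

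*Protocol*

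**What the plan says.** Section 6.2.1 of the protocol describes three time-stamped streams recorded over the same 20 minutes:

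- The reference stream is the operator's, "collected by the operator pressing a foot pedal each time a movement is noted".
- The maternal stream is "collected by the mum pressing a button when she felt the movement".
- For the third stream, "The device will collect movements when the piezoelectric fabric is distorted by fetal movements". Software then filters the voltage and converts it to binary events, with a training subset used for that step.

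The streams are matched "allowing for a degree of error (±500ms) to account for the reaction time of the mother and sonographer". That is the only matching rule given. It makes no distinction between the device-operator and mother-operator pairs and does not mention shifting a stream for its lag.

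Section 9.1.1 builds the primary outcome on the matches: a yes/no value for device and for mother, "indicating whether each of the scan operator movements was successfully identified". The planned primary test is stated as follows: "McNemar's test of paired proportions will be conducted to detect a difference in the proportions of movements detected by the device compared with the mother". It is run visit by visit. Section 9.1.2 compares the two positive predictive values (PPVs) using the same matches.

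**The concern.** The tolerance is justified by the reaction times of two people, but it also governs a comparison in which only one of them takes part. In the mother-operator gap, two human delays are subtracted and similar delays largely cancel. In the device-operator gap there is no second human delay to subtract, so the operator's delay remains almost in full, reduced only by whatever latency device processing adds.

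If a match needs the pairwise gap to be within 500 ms, a true device detection is scored as missed when the operator's net delay exceeds 500 ms. A true maternal detection is scored as missed when the two human delays differ by more than 500 ms. These two loss rates need not be equal, and the primary test compares what is left after them. An unmatched true detection also counts as a false positive, so it lowers the PPV of that source. Collecting more movements does not remove a bias of this kind.

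**Working it through.** **Planned figure.** Section 9.1.1.1 has an "assumed sensitivity rate of 44% for the pregnant mothers", and for the device, "we assumed a sensitivity rate of 60% for the wearable device". The difference is d = 0.60 − 0.44 = 0.16. At the minimum phi, joint detection is 0.60 + 0.44 − 1 = 0.04, so the discordant cells are 0.56 and 0.40 and their sum is ψ = 0.96. With two-sided 5% and 90% power, n = (1.960 + 1.282)² × 0.96 / 0.16² = 394.03, rounded up to the stated 395. This treats every true detection as matched.

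**Matching model.** Let O be the operator's delay, M the mother's and L the device latency, all normal and independent.

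- Device capture = P(|O − L| ≤ 500 ms)
- Mother capture = P(|M − O| ≤ 500 ms)
- Recorded sensitivity = true sensitivity × capture

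The documents give no delays, so all delays below are assumptions. L is set to 0 in the table.

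| Assumed delays, mean (SD), ms | Device capture | Mother capture | Recorded, device vs mother | Difference (points) |
|---|---|---|---|---|
| Both 300 (100) | 97.7% | 100.0% | 58.6% vs 44.0% | +14.6 |
| Both 400 (150) | 74.8% | 98.2% | 44.9% vs 43.2% | +1.7 |
| Operator 500 (200), mother 600 (300) | 50.0% | 81.8% | 30.0% vs 36.0% | −6.0 |
| Operator 300 (150), mother 1000 (400) | 90.9% | 31.7% | 54.5% vs 14.0% | +40.5 |

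Worked example, third row. Device: Φ((500 − 500)/200) = 0.50. Mother: the mean gap is 100 and its SD is √(200² + 300²) = 360.6, so capture is Φ(400/360.6) − Φ(−600/360.6) = 0.866 − 0.048 = 0.818. Excluding negative delays raises the mother's capture to about 83% and her recorded figure to about 37%.

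Giving the device latency a mean of 0 and an SD of 50 ms changes little: the first two differences become +13.8 and +1.0.

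**Break-even.** The difference vanishes when device capture / mother capture = 0.44/0.60 = 0.733. With equal human delays, this occurs at a mean of about 0.41 to 0.46 s for SDs of 0.1 to 0.3 s.

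**Equal true sensitivities.** Take 0.50 for both sources, 395 movements and independent detections. Capture of 90% vs 100% gives recorded 0.45 vs 0.50, so ψ = 0.45 + 0.50 − 2 × 0.225 = 0.50. The rejection probability is Φ((√395 × 0.05 − 1.96 × √0.50)/√(0.50 − 0.05²)) = Φ(−0.556), or 29%, where 5% is intended. Capture of 75% vs 100% gives 94%.

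**Chance matches.** For k events in 1200 s and a total window of w seconds, the chance of a coincidental match is about 1 − exp(−kw/1200). At ±500 ms (w = 1) it is 0.8% for 10 events and 8% for 100. At ±2 s (w = 4) it is 28% for 100.

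**The case against.** The strongest reply is that every delay above is assumed. If both observers respond in about 300 ms with little spread, the loss is 1 to 2 points and the rule does no real harm. That stands: this is a risk, not a demonstrated bias.

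A reader might infer that device events always lead the pedal, so that half of the symmetric window is useless. The documents do not support this. They do not say which point of the voltage signal is stamped or what latency the filtering adds. Movements also have duration, and section 6.2.1 records a further event when one persists. If the device registers a span, a late pedal press could still overlap it, and the device loss computed above would be too large.

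A reader might also infer that the trial will probably rank device and mother the wrong way round. That does not follow either. Section 9.1.1.1 chose 60% and 44% to be conservative: it expects the device to detect 0.8 to 0.9 of movements, and 0.44 is the top of the maternal range quoted. In the third scenario, 0.8 to 0.9 × 50% gives 40-45%, against 0.44 × 83% = 37%, so the difference shrinks without reversing. That reassurance belongs to that scenario; a longer operator delay would lower the device figure further.

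The sentence can be read in other ways. If ±500 ms applied to each human time-stamp, mother-operator gaps of up to 1 s would match while the device limit stayed at 500 ms, so the inequality would remain. If it meant residual error after alignment, most of the concern would go, but no alignment is stated.

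Finally, matching detail often sits in a statistical analysis plan, which is not shown here. The absence of an algorithm is therefore no fault. The point is limited to the numeric rule that the protocol itself places in the primary endpoint definition.

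**Conclusion.** The point holds in a limited form. One ±500 ms tolerance, stated without lag alignment, is applied to two pairs whose delays have different structures. Read as a limit on each pairwise gap, it can lose true detections at different rates for device and mother, which affects the primary sensitivity comparison and both PPVs.

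Neither the size nor the direction can be established from the documents. Over the assumed delays, a true difference of 16 points is recorded as anything from about 15 (almost unaffected), through about 1 to 2 (hidden), to −6 (reversed), and it is enlarged if the mother is much slower than the operator. The reversal shown depends on the 60% vs 44% planning values and on an operator delay averaging 500 ms. All of these results assume normal delays, instantaneous events and negligible device latency. The rule should be amended because the exposure is in the primary outcome and the remedy is cheap.

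**What to change.** In section 6.2.1, state that:

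- the pedal-minus-device and pedal-minus-button lags will be estimated in the training women, using a wide provisional window to identify pairs;
- each stream will be shifted by its median lag;
- the offsets and one common window width will be locked before the remaining data are matched.

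A common width is preferable to a separate width for each source, because unequal widths would create unequal chance matching.

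Repeat the primary and PPV analyses at wider windows, for example ±1 s and ±2 s. Beside each, report the chance-match rate obtained from time-shifted traces. That rate is a descriptive check only: subtracting it from a proportion cannot correct the paired yes/no outcomes that McNemar's test uses.

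The cost is re-processing of time-stamps already recorded, with no change to visits or participants. There are two drawbacks. The three training women supply only about 30 movements, so the lag estimates will be rough. Wider windows also admit more chance matches, and this can be substantial if the device registers many events (about 28% at ±2 s with 100 events in 20 minutes).

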# 6.2.2 Secondary Endpoints/Outcome Measures

The first secondary endpoint of the study is the proportion of movements detected by the device and by the pregnant women that are true-positives, that is those that are also identified by the scan operator, at weeks 32, 34, 36, and 38 of pregnancy. These are the positive predictive values of the device and the pregnant women, which will help understand the extent of false-positive movements and their impact on the usefulness of the wearable device.

The second secondary endpoint of the study is the acceptability of wearing the device as self-reported by the women in a bespoke end of study questionnaire. Please see Appendix 3.

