#### 9.1.2 Analysis of Secondary Endpoints

The analysis of the first secondary endpoint will be a comparison to the proportions of movements detected by the device and the pregnant women that are true-positives, i.e., those that are also identified by the scan operator, at each of weeks 32, 34, 36, and 38 of pregnancy separately. A z-test of independent proportions will be conducted to detect a difference in the positive predictive value rates for the device compared with the mother, if such a difference exists.

The same analysis will be repeated for the week 32, 34, 36 and 38 visit movements separately. Again, the movements at a particular visit (either week 32, 34, 36 or 38) will be collated across the pregnant women for analysis, and the repeated foetal movements for a given pregnant woman during a particular scan will be treated as independent.

For the second secondary analysis, frequency tables/summary statistics of the responses to the self-reported acceptability questions will be provided please see Appendix 3. The

Formatted: Not Highlight

Formatted: Superscript, Not Highlight

Version 2 April 12th 2021

proportion of women agreeing that the device was acceptable to wear will also be reported, with corresponding 95% confidence interval.

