#### 9.7 Inclusion in Analysis

All data collected from scanning whilst wearing the data will be analysed. Even if the patient leaves the study prior to completing all 4 scans.

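### Acceptability is asked only at end of study, so women who leave early may give no answer and the reported proportion can be biased, most plausibly upwards

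*Protocol*

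**What the plan says.** Establishing acceptability is one of two secondary objectives (Protocol 5.2). Section 6.2.2 measures it as "self-reported by the women in a bespoke end of study questionnaire", and the synopsis says the same. The text shown describes no other acceptability measurement.

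For the analysis, 9.1.2 provides frequency tables or summary statistics of the answers. It adds that the "proportion of women agreeing that the device was acceptable to wear will also be reported", with a 95% confidence interval. It does not state the denominator.

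Section 9.1.1.1 expects losses: "Allowing for a drop-out rate of approximately 20%, a final sample size of 54 subjects".

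Two places deal with women who leave early:

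- Section 6.6 keeps the scans done before an early birth and records the reason for any withdrawal in the CRF. It arranges further contact after withdrawal only where the cause was an adverse event.
- Section 9.7 says "All data collected from scanning whilst wearing the data will be analysed", including for women who do not complete all four scans.

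Neither mentions the questionnaire. Section 6.1 plans a telephone call at 6 to 8 weeks after birth, but the text does not link it to the questionnaire.

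**The concern.** Acceptability is an opinion about wearing the garment, and disliking the garment is one plausible reason to stop. Section 6.6 lists withdrawal of consent, non-compliance and adverse events among the routes out, and 8.1.2 gives a contact rash as its example of a device effect. Consent and the first scan share a visit (6.1), and the garment is worn during the scans (7.1). A woman who drops out after that visit has therefore worn it and has an opinion to give.

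If the questionnaire reaches only women still in the study at its end, the reported proportion describes them and not everyone who wore the device. A confidence interval computed on the respondents covers sampling error among respondents only, and says nothing about the women who were not asked. An analysis plan can set rules for missing answers, but it cannot recover answers that were never collected. That is why the time of collection matters at protocol stage.

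**Working it through.** **Inputs from the protocol (9.1.1.1).** 395 movements per visit, at least about 10 movements per woman per scan, 3 women for training, about 20% drop-out, 54 recruited.

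**Reproducing the plan's figure.** 395 / 10 = 39.5, rounded up to 40. Then 40 + 3 = 43, in line with "taking the number of subjects in the study to 43". Then 43 / (1 − 0.20) = 53.75, rounded up to 54. The stated 54 is reproduced. The women allowed for as lost number 54 − 43 = 11, and 11/54 = 20.4%.

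**Assumptions.** The protocol gives no acceptability rate, so every rate below is assumed. I also assume that all 11 women lost have worn the garment and give no answer, and that the training women are asked like the others.

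**Bounds.** Let N be the women recruited, m the number without an answer, and k the number agreeing among the N − m respondents.

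- Reported proportion: k / (N − m)
- Lower bound for all N (no leaver agrees): k / N
- Upper bound for all N (every leaver agrees): (k + m) / N

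| Without answer | Reported | Wilson 95% CI | Lower bound | Upper bound |
|---|---|---|---|---|
| 11 | 39/43 = 90.7% | 78.4 to 96.3 | 39/54 = 72.2% | 50/54 = 92.6% |
| 11 | 34/43 = 79.1% | 64.8 to 88.6 | 34/54 = 63.0% | 45/54 = 83.3% |
| 11 | 30/43 = 69.8% | 54.9 to 81.4 | 30/54 = 55.6% | 41/54 = 75.9% |
| 5 | 44/49 = 89.8% | 78.2 to 95.6 | 44/54 = 81.5% | 49/54 = 90.7% |

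In the first row the reported figure could be too high by 90.7 − 72.2 = 18.5 points or too low by 92.6 − 90.7 = 1.9 points. In the first two rows the lower bound falls below the reported interval. In the last two it falls inside.

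**Between the extremes.** The bias equals (m / N) × (agreement among completers − agreement among leavers). With m / N = 11/54 = 0.204 and 90% agreement among completers:

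- leavers at 90%: 0.204 × 0 = 0 points
- leavers at 50%: 0.204 × 40 = 8.1 points upwards
- leavers at 0%: 0.204 × 90 = 18.3 points upwards
- leavers at 100%: 0.204 × (−10) = 2.0 points downwards

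**The case against.** The strongest reply is that the protocol nowhere excludes early leavers from the questionnaire. End of study could mean each woman's own exit, or the postnatal call that 6.1 plans and 6.5 counts towards the end of the trial. A woman who gives birth early could still be asked then. The questionnaire (Appendix 3) and the content of the visit flowsheet (Appendix 1) are not in the text available, and either might settle who is asked and when. Section 9.7 sets a rule for scan data and does not rule out questionnaire answers from women who leave. The denominator and the handling of missing answers are ordinary content for an analysis plan.

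The bias itself is also not shown. The garment is described as worn during four 20-minute scans, so leaving because of discomfort is possible but not documented. Early birth, ineligibility and loss to follow-up may have nothing to do with acceptability. The worst case needs all 11 women to go unasked and all to disagree.

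Most of this stands. A reader might infer that the plan restricts the proportion to completers, or places the questionnaire after the fourth scan. The text says neither. A reader might also infer that the figure is certain to be too high. It is not, since the bias can be nil or run slightly downwards.

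What the reply does not remove is that the text shown fixes one collection time, expects about a fifth of the women to drop out, provides for their scan data, and makes no provision for obtaining their answers. That the present wording is compatible with asking them does not ensure that they are asked.

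**Conclusion.** The point holds as a gap in collection. A site following the text shown could lose the acceptability answers of women who stop early, and the reported proportion could then be biased. Upwards is the most plausible direction, because dislike of the garment is a possible reason to leave, but the documents do not establish it.

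The size depends on assumed rates. A reported 91% would be compatible with 72% to 93% among all 54 women if 11 give no answer. The range narrows to 81.5% to 90.7% around a reported 89.8% if only 5 are missing. A gap of about 18 points is a limit, not an estimate.

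Severity is minor. This is a pilot (9.1.1), and acceptability is summarised descriptively, without a hypothesis test or success threshold. It is still worth correcting because it bears on one of only two secondary objectives and the remedy is nearly free. The missing denominator alone would not carry the point, since an analysis plan could supply it.

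**What to change.** - **Section 6.2.2:** state that the questionnaire is offered at the last garment use or at withdrawal, whichever applies, with the planned postnatal call as a fallback for women not reached then. If an appendix already says this, a cross-reference is enough.
- **Section 9.1.2 (or the analysis plan):** report the proportion agreeing together with the number of women who wore the device at least once and the number who did not respond. Add a sensitivity figure that counts non-responders as not agreeing.

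The cost is a line or two of text in each place and about 11 more short questionnaires at the planned drop-out. The headline proportion may come out lower.
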